#### **8.14. Study Termination Criteria**

The sponsor may terminate this study prematurely, either in its entirety or at any site, for reasonable cause provided that written notice is submitted in advance of the intended termination. The investigator may also terminate the study at his/her site for reasonable cause, after providing written notice to Lohocla Research Corporation in advance of the intended termination. Advance notice is not required by either party if the study is stopped due to safety concerns. The FDA may stop the study at any time as well. If the FDA notifies the sponsor to stop the study, then the sponsor will notify the site of this action.

## 9. STUDY ENDPOINTS

### 9.1. Safety Endpoints

Safety endpoints include:

- AEs
- Stool Consistency Questionnaire indicative of a GI AE
- GI Signs and Symptoms Checklist indicative of a GI AE
- Clinical laboratory data
- ECG results
- FOBT results
- Vital signs
- Rate of urine output (24 hrs)

### 9.2. PK Endpoints

PK endpoints include:

**AUCt:** Area under the plasma concentration-time curve from time 0 to the time (t) of last quantifiable concentration (Ct) calculated by the log-linear trapezoidal rule.

**AUC∞:** Area under the plasma concentration-time curve from time 0 extrapolated to infinity. The terminal area from Ct to infinity was calculated by using the approximation as Ct/λz, thus AUC∞ = AUCt + Ct/λz.

**Cmax:** The maximum observed plasma concentration.

**tmax:** The observed time to reach maximum plasma concentration.

**λz:** The terminal-phase exponential rate constant as calculated from the negative slope of the regression line for the terminal linear portion of the LN transformed plasma concentration versus time curve.

**t1/2:** The apparent terminal exponential half-life, calculated as ln(2)/λz.

## 10. SAFETY MONITORING PLAN

Safety monitoring will be conducted throughout the study; therefore, safety concerns will be identified by continuous review of the data by the PI, clinic staff, clinical monitor, medical monitor, and the sponsor.

**Study Safety Management:** The IRB, Medical Monitor, PI, clinical monitors, and Lohocla Research Corporation will review any safety concerns throughout the trial. In addition, the UCSD DSMB will participate in this study. The roles of these individuals/committee are described below.

**Medical Monitor:** A Medical Monitor will be appointed by the sponsor for the study. The Medical Monitor will be available for making recommendations to the investigator and the sponsor on the severity of any SAEs, and the relatedness to the study interventions, and if laboratory excursions or other AEs meet the criteria for stopping escalation or stopping the study. The Medical Monitor will also be responsible for tracking and assessing trends in the AEs reported.

**Clinical Monitors:** All investigators will allow representatives of the contract research organization (Fast-Track Drugs and Biologics, LLC) to periodically monitor, at mutually convenient times during and after the study, all study data. These monitoring visits provide the clinical monitors and the sponsor with the opportunity to evaluate the progress of the study and to obtain information about potential problems. The monitors will assure that submitted data are accurate and in agreement with any paper source documentation used, verify that investigational products are properly stored and accounted for, verify that subjects' consent for study participation has been properly obtained and documented, confirm that research subjects entered into the study meet inclusion and exclusion criteria, and assure that all essential documentation required by Good Clinical Practices (GCP) guidelines are appropriately filed.

Monitors will conduct a site initiation visit prior to the start of the study. At this visit, they will assure that proper study-related documentation exists, assist in training investigators and other site personnel in study procedures and GCP guidelines, confirm receipt of study supplies, and assure that acceptable facilities are available to conduct the study.

Routine monitoring visits by the clinical monitors and the sponsor will be scheduled at appropriate intervals but more frequently at the beginning of the study. A monitoring visit soon after the first two subjects have been treated is planned. At these visits, the monitors will verify that study procedures are being conducted according to the protocol guidelines, monitor eCRFs against source documents, review AEs and SAEs, and perform drug accountability. At the end of the study, they will confirm that the site has the appropriate essential documents on file, advise on storage of study records, and inspect the return and destruction records for unused investigational products.

**Sponsor Site Visits:** All investigators will allow the sponsor full access to study records during site visits by the sponsor. Visits by the sponsor will be made at a mutually convenient time and will be scheduled in advance.

**DSMB:** The UCSD DSMB will meet prior to the start of the study, and after each cohort completes the study. As each cohort completes the study, a Fast-Track unblinded statistician will generate the appropriate tables and listings including PK data and a Fast-Track physician will

compile this safety data and prepare a safety report for presentation to the DSMB in accordance with the Operating Charter and planned analyses. *Ad hoc* meetings will be convened if SAEs occur that are considered at least possibly related to the investigational product or clinical, laboratory, or AE findings meet any of the stopping criteria (see section [8.12.2](#)).

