To minimize risks to study subjects, an enteric coated tablet of kindolor tosylate has been developed that does not dissolve in solutions that mimic gastric fluid but does dissolve in solutions that mimic the intestinal environment that will be used in this first-in-humans study. The starting dose is conservatively 80-fold lower than the HED in the most sensitive nonclinical species (rats). Gastric toxicity will be specifically monitored in accordance with the plan in Section 11.1.5. There is an extensive array of clinical laboratory tests consistent with first-in-human studies. Although there is no evidence of cardiovascular toxicity in *in vitro* and *in vivo* studies, vital signs and ECG parameters will be closely monitored throughout the 5-half-life period after drug dosing.

Kindolor tosylate may have phototoxic potential that may appear as an exaggerated sunburn reaction (reddening and swelling) or in severe cases, vesicles, blisters and bullae may occur. In minipigs, the average elimination half-life of kindolor ranged 3.21 to 4.36 hours depending on the dose. Five half-lives, which approximates 99% elimination of circulating levels is 22 hours for kindolor with a 4.36-hour half-life. Therefore, subjects will not be exposed to sunlight while in the Phase 1 unit and will be cautioned to limit exposure to direct sunlight after release and to apply a sun protectant lotion to exposed areas of the skin after release for at least another 24 hours.

Safety data will be monitored by the principal investigator (PI), other study physicians, the medical monitor, and clinical monitors throughout all aspects of the study. The DSMB will review the safety data (AEs, vital signs, ECG, and clinical laboratory data) as each cohort completes the final 7-day safety visit and will approve escalation to the next dose before any additional subject cohorts are enrolled.

The main procedure risks are related to the multiple blood draws (total volume of blood to be collected for PK and other clinical laboratory tests is not expected to exceed 168 mL). If an endoscopy is performed, its most severe risks include infection, perforation of the esophagus or stomach, and bleeding.

There is a minor risk of loss of confidentiality; however, controls are in place to maintain protected health information securely both in paper copy and electronically. All clinical specimens will be deidentified prior to storage.

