### **8.13.2. Dose Continuation, Dose Escalation and Study Stopping Criteria**

Continuation of dosing within a cohort, or dose escalation to sequential cohorts will stop when either:

- a) The highest dose is reached or,
- b) Clinical/laboratory/AE findings meet any of the following stopping criteria:
  - i. Two or more subjects on active medication have clinical laboratory values meeting the criteria of moderate (Grade 2) intensity
  - ii. Two or more subjects on active medication experience moderate AEs of the same type (within the same MedDRA SOC)
  - iii. One or more subjects on active medication experiences any clinical laboratory value meeting the criteria of severe (Grade 3 or 4) intensity or an AE is determined to be severe in intensity
  - iiii. Any subject has a positive FOBT
- c) The mean kindolor systemic exposure levels exceed  $AUC(T_{last})=87,550$  ng.h/mL or  $C_{max} > 13,490$  ng/mL in a single subject in a cohort.
- d) The DSMB recommends stopping escalation after review of all the data from each cohort.

The maximum tolerated dose (MTD) will be considered the highest dose where no active medication subjects meet the study stopping criteria.

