#### 11.1.7. Classification of Adverse Event Intensity and Relationship to Investigational Product

The severity of AEs or SAEs will be in accordance with the FDA's "Toxicity Grading Scale for Healthy Adult and Adolescent Volunteers Enrolled in Preventive Vaccine Clinical Trials". For those not listed in the guidance, the following criteria will be used:

Mild:	An event that is usually transient, requiring no special treatment, and does not generally interfere with the subject's daily activities.
Moderate:	An event that interferes with usual activities of daily living, causing discomfort but poses no significant or permanent risk of harm to the subject. The event is usually ameliorated with additional specific therapeutic intervention.
Severe:	An event that interrupts usual activities of daily living or significantly affects clinical status. The event poses a significant risk of harm to the subject and hospitalization may be required, and typically requires intensive therapeutic intervention.

However, as gastric AEs are a potential concern, and the toxicity grading scale stated above, does not cover some of the more serious gastric AEs such as gastritis and gastric ulcer, the Common Toxicity Criteria for Adverse Events Grading Scale (version 5.0) will be used for the severity of these AEs.

The investigator must assess relationship to the investigational product based on the following criteria:

Unrelated:	The subject did not receive the investigational product, the temporal sequence of the AE/SAE onset relative to administration of the investigational product is not reasonable, or there is another obvious cause of the AE/SAE.
Unlikely:	There is evidence of exposure to the investigational product but there is another more likely cause of the AE/SAE.
Possible:	There is evidence of exposure to the investigational product, the temporal sequence of the AE/SAE onset relative to administration of the investigational product is reasonable, but the AE/SAE could have been due to another equally likely cause.
Probable:	There is evidence of exposure to the investigational product, the temporal sequence of the AE/SAE onset relative to administration of the investigational product is reasonable, and the AE/SAE is more likely explained by the investigational product than by any other cause.

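### An at least possibly related SAE calls an ad hoc DSMB meeting, but no written rule pauses dosing in the cohort until it meets unless a separate stopping criterion is also met

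*Protocol*

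**What the plan says.** Protocol section 10 gives two alternative grounds for an unscheduled DSMB review. On the first, ad hoc "meetings will be convened if SAEs occur that are considered at least possibly related to the investigational product". The second is that findings meet a stopping criterion (cited there as 8.12.2, its number in the table of contents; the text is in 8.13.2). Section 10 sets no deadline for the meeting and says nothing about dosing in the meantime.

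The stopping rule does reach inside a cohort: "Continuation of dosing within a cohort, or dose escalation to sequential cohorts will stop when either" one of its listed conditions is met. A single clinical AE stops dosing only under b.iii, which requires a severe laboratory value "or an AE is determined to be severe in intensity". Item d) applies when "The DSMB recommends stopping escalation after review of all the data from each cohort". Section 4.9 has the DSMB review each cohort after its final safety visit and says that it "will approve escalation to the next dose before any additional subject cohorts are enrolled".

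Two other parts of section 10 bear on the point. A physician of the contract research organization is to "prepare a safety report for presentation to the DSMB in accordance with the Operating Charter and planned analyses", so a Charter exists, but it is not among the documents. The Medical Monitor is available for "making recommendations to the investigator and the sponsor on the severity of any SAEs".

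**The concern.** Section 10 treats a related SAE as reason enough to call the DSMB, whether or not a stopping criterion is met. The purpose of such a meeting is to judge whether it is safe to continue. Yet the rule that controls dosing does not recognise the event that calls the meeting. A site that follows the text exactly could dose further subjects of the same cohort, at the same dose, before the DSMB has looked. Item d) adds a second weakness. As worded, it gives effect to a DSMB recommendation on escalation after a cohort's data are complete, so a recommendation made mid-cohort to stop dosing has no stated effect. In a first-in-human trial the dosing team should not have to improvise either step.

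**Working it through.** **Figures in the plan.** The plan gives none on this point. Its only design probabilities (protocol 12.4, SAP section 7) reproduce from 1 − (1 − p)^6: 46.9%, 62.3%, 73.8% and 82.2% at p = 10%, 15%, 20% and 25%, against the stated 47%, 62%, 74% and 82%. Nothing below uses them.

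**Step 1: is there a hold?** Take one SAE, at least possibly related, graded below severe, with no other finding, and test it against each provision.

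| Provision | What it does | Holds dosing here? |
|---|---|---|
| Section 10, ad hoc meeting | Calls the DSMB | No, meeting only |
| 8.13.2 b.i | Two active subjects with Grade 2 laboratory values | No |
| 8.13.2 b.ii | Two active subjects with moderate AEs in one SOC | No, single event |
| 8.13.2 b.iii | One severe AE or Grade 3/4 laboratory value | No, below severe |
| 8.13.2 b.iiii and c) | Positive FOBT; exposure limits | No, absent by assumption |
| 8.13.2 d) | DSMB advice on escalation after cohort review | Not written for mid-cohort |
| 11.1.5 | Confirmed gastric erosion, ulcer or bleeding stops the study | No, absent by assumption |
| Synopsis, 4.9, section 5 | DSMB review of each completed cohort | No, cohort already dosed |
| 8.5 | 24-hour sentinel watch; two subjects a day at most | No SAE-based go/no-go |
| 11.1.9.1 | SAE notification within 24 hours | No |
| 8.14 | Sponsor or investigator may stop | Discretionary |
| SAP 9.11 | Interim safety analysis per completed cohort | No |

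**Step 2: can the case occur?** Section 11.1.3 has the investigator rate seriousness, relationship and severity separately. Under 11.1.2 an important medical event can be serious without hospitalization if it may need intervention to prevent a listed outcome. Under 11.1.7 a moderate event is one usually improved by specific treatment. The overlap is narrow, because the same definition describes a moderate event as "causing discomfort but poses no significant or permanent risk of harm to the subject", but it is not empty.

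**Step 3: how many could be dosed first?** Inputs: 6 subjects remain after the sentinel pair, at most 2 dosed per day, with intake only after the 24-hour watch (8.5); those 6 are randomized 5 active to 1 placebo (8.7.1). The delay m, in days from knowledge of the event to a meeting held before that day's dosing, is an assumption.

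*Event in the active sentinel.* Dosed on day S; event known at the end of the watch, S+1; intake from S+1; the others dosed on S+2, S+3 and S+4. Number dosed before the meeting on S+1+m: n = min(6, 2 × max(0, m − 1)). Expected active = n × 5/6.

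| m (days) | Dosed | Expected active |
|---|---|---|
| 1 | 0 | 0 |
| 2 | 2 | 2 × 5/6 = 1.67 |
| 3 | 4 | 4 × 5/6 = 3.33 |
| 4 or more | 6 | 6 × 5/6 = 5 |

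*Event in an active member of the first pair after the sentinels, known on the dosing day D.* Four subjects remain, dosed on D+1 and D+2. For a meeting on D+m, n = min(4, 2 × max(0, m − 1)). The other five of the six are 4 active and 1 placebo, so expected active = n × 4/5: m = 1 gives 0; m = 2 gives 2 (1.6 active); m of 3 or more gives 4 (3.2 active).

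Both sets of counts are upper limits. Slower dosing lowers them.

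**The case against.** The strongest case on the other side is that the gap hardly arises in practice. Many SAEs would be graded severe and so meet b.iii. Positive FOBT and confirmed gastric injury stop dosing or the study at any grade, which covers the main expected toxicity. Safety data are under continuous review, SAEs reach the sponsor within 24 hours, the Medical Monitor advises on severity and on whether criteria are met, and either party can stop without notice for safety. The Charter is a natural home for a rule on interim holds. All of this stands. It makes the case rare, and it may reduce the point to a missing cross-reference. None of it is a required pause in the supplied text.

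Three stronger readings are tempting, and the documents do not support them:

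- *A short hospital admission graded moderate proves the gap.* The definitions in 11.1.7 are a fallback. The primary scales are the FDA toxicity scale and, for some gastric events, CTCAE version 5.0; neither is supplied. SAP 5.2 also mentions hospitalization in its Grade 4 definition, and subjects are already confined until Day 3. The route through an important medical event does not need this example.
- *The DSMB can act only on escalation.* The synopsis and section 5 let it recommend stopping the study. That power is described for completed-cohort review, so it does not supply a mid-cohort pause, but it is wider than item d).
- *The trial has no hold at all.* That cannot be said without the Charter.

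**Conclusion.** The point holds in a limited form. In the protocol and SAP as supplied, an at least possibly related SAE obliges the DSMB to meet but does not oblige the site to stop dosing the cohort, unless the event also meets 8.13.2 or 11.1.5. The exposed case is one such SAE graded below severe. Its frequency cannot be estimated from the documents, and none is claimed.

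The size is a count of exposure: 0 further subjects if the meeting is the next day, rising to 6 (5 active) if it is 4 or more days after an event in the active sentinel becomes known. This assumes dosing at the cap, no discretionary pause and no hold in the Charter. A reader might take the 6 as an expected outcome or a measure of risk; it is neither. This is a cheap improvement to subject safety and does not show that the present safeguards fail.

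**What to change.** 1. State in section 10 and in 8.13.2 that any SAE considered at least possibly related to the investigational product, whatever its grade, suspends further dosing from the time the site learns of it until the ad hoc DSMB meeting gives its written recommendation. In 8.13.2 this should be a separate paragraph describing a temporary hold, not a new item in list b), so that the MTD definition, which depends on the stopping criteria, is unchanged.
2. Have the sponsor and DSMB set a target time for that meeting, so that the hold is not open-ended.
3. Extend 8.13.2 d) to a DSMB recommendation to stop dosing within a cohort after an ad hoc review.
4. If the Charter already imposes the hold, cite it in section 10 in place of item 1.

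The unblinded statistician can give the DSMB the assignment, and the recommendation need not disclose it, so the site stays blinded. The two-subject threshold in b.ii is untouched.

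The cost is a few sentences of amendment and a pause even when the affected subject proves to be on placebo. Anyone whose 30-day screening window lapses during the pause needs full re-screening, because 8.5 does not allow an extension.

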## **11. ASSESSMENT METHODS**

All study assessments will be performed at the visits and time points outlined in the Schedule of Assessments (Table 6); the following sections outline the details and procedures associated with the assessments. All assessments will be recorded on a source document and transcribed into electronic case report forms (eCRFs).

### **11.1. Adverse Events and Serious Adverse Events**

The investigator and study site staff are responsible for the detection, documentation, classification, reporting, and follow-up of events meeting the definition of an AE or SAE.

#### **11.1.1. Adverse Event Definition**

An AE is any untoward medical occurrence in a clinical investigation subject administered a pharmaceutical product and may not necessarily have a causal relationship with the administered treatment. An AE can therefore be any unfavorable and unintended sign (including a clinically significant laboratory abnormality), symptom, or disease temporally associated with the use of an investigational product, whether or not related to the investigational product. Pre-existing conditions, diseases, or disorders are not considered AEs unless there is a change in severity or frequency.

#### **11.1.2. Serious Adverse Events and Serious Unexpected Adverse Events Definition**

An SAE is any untoward medical occurrence that meets one of the following:

- Results in death
- Is life-threatening (at the time of the event)
- Requires inpatient hospitalization or prolongation of existing hospitalization
- Results in persistent or significant disability/incapacity
- Is a congenital anomaly/birth defect

A serious and unexpected AE is an SAE that is not identified in nature, intensity, or frequency in the risk information included in the Product Label for the drug.

Important medical events that may not result in death, be life-threatening, or require hospitalization may be considered a serious adverse drug experience when, based upon appropriate medical judgment, they may jeopardize the study subject and may require medical or surgical intervention to prevent one of the outcomes listed in the definition.

#### **11.1.3. Methods/Timing for Assessing, Recording, and Analyzing Safety Endpoints**

AEs will be assessed starting after the first administration of investigational product until the final follow-up visit. However, SAEs will be collected from the time of informed consent onward. General symptoms will be collected via an open-ended question: "How have you been feeling since your last visit or the last time we spoke?"

AEs will be documented in the source records and recorded on the eCRFs using accepted medical terms and/or the diagnoses that accurately characterize the event. When a diagnosis is

known, the AE term recorded on the eCRF will be the diagnosis rather than a constellation of symptoms. The investigator will assess all AEs for seriousness, relationship to investigational product, and severity. When an event has not resolved by study closure, it will be documented on the AE eCRF as “ongoing”.

All AEs, including clinically significant abnormal findings on laboratory evaluations, regardless of severity, will be followed by study physicians until satisfactory resolution (the event either resolved or stabilized and is not expected to resolve in the near term). AEs must be reported up to 1 week after investigational product administration. At the final clinic visit, AEs will be recorded and followed to resolution only if they are serious, or if the study physician assesses them to be clinically significant.

